pregnancy obstetric provider. The intervention group will continue the RT-CGM device and will be instructed to continue fingersticks only when concerned for hypoglycemia and/or inaccuracy of sensor. The control and intervention groups will follow-up serially for the duration of pregnancy (see schematic for visits below). The control group will wear the blinded CGM at serial timepoints throughout pregnancy and the intervention group will have serial download of RT-CGM. Participants will also have labs checked every 8 weeks which will include HbA1C and fructosamine at beginning and end of the study. It is estimated that participants will be enrolled at 24-28 weeks and have 4 visits (estimating a pregnancy duration of 40 weeks). Some participants may receive a diagnosis of gestational diabetes earlier and thus have more sessions. Maternal and neonatal outcomes will be abstracted from delivery records.

[figure not shown]

Figure 1: Study Design Schematic: N=100 Control N=50 GDM Intevention: GDM N=50

*Approximate Total duration of CGM use would be 14-22

**see timeline for measures appendix B

Figure 2: Timeline for Visits Based on High Risk for Gestational Diabetes and Typical Risk

		Screening Visit 0	Visit 1b High risk	Visit 1a	Visit 2++	Visit 3	Visit 4*
Gestational age Intervention	High Risk	14	20-22 weeks	24-30 weeks	30-32 weeks	34-36 weeks	38-40 Weeks

Gestational age Intervention	Typical Risk	24-28	N/A	24-30 weeks	30-32 weeks	34-36	38-40 Weeks
Gestational age Control	High Risk	14	14-16 weeks	24-30 weeks	30-32	34-36	38-40 Weeks
Gestational age Control	Typical Risk	24-28	N/A	24-30 weeks	30-32 weeks	34-36	38-40 weeks

+++ visits will be a minimum of 2 weeks apart

*38-40 week data only collected in participants that make it to 38- 40 week gestational age

Screening/Pre-Intervention Visit(week 0):

Consent (appendix R) will be obtained prior to any screening procedures being completed, and conducted in a quiet room or private televisit. Participant will be given ample time to ask questions, and a copy of the signed consent form will be given prior to start of screening visit. Participants will fill out a contact form, including emergency contact. Study staff will review medical history and medications, pregnancy history, patient's mother's pregnancy history, sleep history, and lipid profile if available (appendix D), as well as all inclusion/exclusion criteria.

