Week 2 (Visit 1a): Gestational Age 14-16 (Early GDM Dx) or 24-28 weeks (Regular GDM Dx)

RT-CGM and meter will be downloaded for intervention group and meter downloaded for the control group. Glucose logs will be collected. All participants will confirm they have completed RN gestational DM education and nutrition appointments per local standard of care. Vital signs, weight and medications and dose will be recorded at each visit and maternal ultrasound results if available (appendix M).

Week 6 (Visit 1b): Gestational Age 20-22 weeks (Early GDM Dx)

RT-CGM and meter will be downloaded for the intervention group and meter downloaded for the control group. Vital signs, weight and medications and dose will be recorded at each visit and maternal ultrasound results if available (appendix M).

Week 6/Week 14 (Visit 2): Gestational Age 30-32 weeks (Both Early GDM Dx and Regular GDM Dx)

RT-CGM and meter will be downloaded for the intervention group and meter downloaded for the control group. Vital signs, weight and medications and dose will be recorded at each visit and maternal ultrasound results if available (appendix M).

The control group will wear blinded CGM for 10 days and return during regularly scheduled OB visit. The study staff will follow up with participants to remind them to return the devices. If for any reason, the CGM device fails to capture at least 3 days of data, the participants may be asked to repeat this measurement at an unscheduled visit.

Week 10/Week 18 (Visit 3): Gestational Age 34-36 weeks (Both Early GDM Dx and Regular GDM Dx)

RT-CGM and meter will be downloaded for the intervention group and meter downloaded for the control group. Vital signs, weight and medications and dose will be recorded at each visit and maternal ultrasound results if available (appendix M).

Questionnaire on nutrition and exercise in pregnancy and satisfaction with CGM and lifestyle changes with CGM.

The control group will wear blinded CGM for 10 days and return during regularly scheduled OB visit. HgA1c and fructosamine will be collected.

The study staff will follow up with participants to remind them to return the devices. If for any reason, the CGM device fails to capture at least 3 days of data, the participants may be asked to repeat this measurement at an unscheduled visit.

Week 14 /Week 22 (Visit 4) Gestational Age 38- 40 weeks (Both Early GDM Dx and Regular GDM Dx)

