- Participants with applicable smart phones may have CLARITY® push notifications on the CLARITY® mobile app about weekly time in range comparison enabled during the study.

- For app users, the “Share and Follow” functionality will be discussed and encouraged (i.e. the study participants are able to invite followers to review their glucose levels).

- For participants using the receiver only, the receiver will be downloaded into the CLARITY® clinic account at each visit. CGM data and reports. RT CGM-Participants will also keep a logbook of their blood sugars for their provider to review.

Control Group

The participants of the control group will perform self-monitored blood glucose testing with a study-provided blood glucose meter, including testing supplies. They will perform capillary blood glucose monitoring as routinely used for patients with GDM, i.e., at least four capillary blood glucose values daily including measurements in a fasting state as well as 1h after starting each meal. The study participants will keep a logbook of their glucose values

Each participant of the control group will be assigned a study blood glucose meter to measure and store their blood glucose values during the study.. A commercially available desktop software used in conjunction with the glucose meter for blood glucose monitoring will be utilized for downloading the meter data at each visit ensuring that dates and times are correct. Blood glucose meters used by the control group will be assessed to establish frequency of testing (overall and per week) as well as percentage of days with less than four measurements per day.

Subjects who got randomized to the control group then decided to withdraw from the study and discontinue their participating in the study will receive an email asking them to fill out a survey questionnaire to explain the main reason and any other reasons for withdrawal from the study. The survey will be sent to subjects’ email through a link from Redcap and it won’t take more than 10 minutes to complete.

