Perception/Satisfaction with CGM and Fingersticks/Meter (Appendices J): The Harvard Joslin Diabetes Center has developed a series of questionnaires on CGM experiences, opinions and expectations that will be given at the end of the intervention and has been adapted for the GDM. Additionally, questions about food changes and activity changes that was created for CGM use(19,20) . Questionnaires have been adapted for use in those using only meter fingersticks and for GDM.

Sleep Questionnaire (appendix Q) The Pittsburgh Sleep Questionnaire is good tool for screening sleep disorders in the population and has been used in pregnancy (22,23)

N: Glucose/CGM Data /Evaluation Measures: The compliance and duration wear for participants with CGM will also be recorded. Glucose dynamics, e.g., average glucose, standard deviation, mean amplitude of glucose excursion (MAGE), time in range % (65 and 140 mg/dL), % high (>140 mg/dL), % low (<64 mg/dL), and severe low % (<54mg/dL) and coefficient of variation (CV) and other statistical measures of glucose variability in those with CGM will be reviewed from the RT- CGM device data at baseline and visit 2-4. Blinded CGM values will be obtained at baseline and visit 2 and 3.

Glucose meter: Compliance with fingersticks 4 times a day will be recorded by average number of fingersticks per day. Glucose data including: average glucose, standard deviation, mean amplitude of glucose excursion (MAGE), time in range % (65 and 140 mg/dL), % high (>140 mg/dL), % low (<64mg/dL), and severe low % (<54mg/dL) will also be recorded.

N:Antenatal Ultrasound Markers: estimated fetal weight (in grams and percentile) using Hadlock scale, Biparietal Diameter, Head circumference, abdominal circumference, and femur length. Amniotic Fluid Index.

O: Delivery Outcomes:

Obstetric Outcomes:

- 1.Gestational age at delivery
- 2.Labor status (spontaneous labor, induced labor, no labor). For induced labor include indication for induction
- 3.Mode of delivery (vaginal delivery, cesarean delivery, operative vaginal delivery) including indication for delivery
- 4.Shoulder dystocia: defined as a delivery that requires additional obstetric maneuvers to release the shoulders after gentle downward traction has failed. SD occurs when either the anterior or, less commonly, the posterior fetal shoulder impacts on the maternal symphysis or sacral promontory

Maternal Outcome:

1. Preeclampsia or GHTN
2. Maternal insulin or medication use

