When the subject enrolls in the study, she will be assigned a unique study number that is not any part of her social security number or other personal identifier. These unique study numbers will be used to identify all information that subjects provide and any information that is collected from their medical records. The unique study numbers will be assigned sequentially according to the order of study enrollment and subjects will be identified by the initials of the group to which they are randomized and 3 numbers according to their entry into the study beginning with 001. Therefore, the first subject randomized to the DMC (control) group will be DMC-001 and the first subject randomized to the DMCGM (intervention) group will be DMCGM-001. A total of 50 DMC and 50 DMCGM subjects will be enrolled.

Although every precaution is being taken to protect participant privacy, breach of confidentiality is always possible. In the unlikely event of a breach of confidentiality, the nature of the research data is not of a sufficiently personal nature to negatively affect employment status, lead to civil/criminal liability, incur financial risks to the study participants, or other risks.

T. Subject Compensation:

Participants will be given \$50 after visit 0 and \$50 after visit 3. Visit 3 compensation will be given to participant upon return of blinded device or RT-CGM download at 34-36 weeks. If lack of CGM data necessitates unscheduled visits, the participant will receive an additional \$25 per visit up to a maximum of \$50 if 2 unscheduled visits are required. Subjects will also have use of the medical devices during the study for free: in the intervention group they will receive a glucose meter and test strips (total 50 test strips for free) to be used as needed. In the control group they will receive a glucose meter and 400 test strips for free if not covered by their insurance. No additional cost will be incurred by subjects.

If extra visits are necessary we will follow the OB clinic guidelines for COVID 19 screening. This money can be used for travel and parking but all study visits are piggy backed to a regular clinic visit so no extra travel or parking is required by the study although visits may be a little longer than usual

U. Appendix:

- A. Educational Material: Real-Time Continuous Glucose Monitoring educational material (A1) or Fingerstick educational material (A2)
- B. Table of Study Measurements
- C. Pre-Screening Checklist Telephone

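### The fixed 400-strip allotment for controls does not last the early-GDM schedule and conflicts with the protocol's own supply statement

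*Combined protocol and SAP*

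**What the plan says.** Section T (Subject Compensation) sets the supply: "In the control group they will receive a glucose meter and 400 test strips for free if not covered by their insurance". The section then closes the topic with "No additional cost will be incurred by subjects". It gives no larger amount for women enrolled early and does not mention resupply.

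Section J (Control Group) sets the testing: "at least four capillary blood glucose values daily including measurements in a fasting state as well as 1h after starting each meal". The same paragraph says the study provides the meter together with its testing supplies, and states no number or limit. Section J also says the meters will be used to establish testing frequency and the share of days with fewer than four tests. Section N (Glucose/CGM Data/Evaluation Measures) uses the same yardstick: "Compliance with fingersticks 4 times a day will be recorded by average number of fingersticks per day".

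Section H (Study Design) sets the duration. The last visit is headed "Week 14 /Week 22 (Visit 4) Gestational Age 38- 40 weeks", the two week numbers being for regular and early diagnosis. The Figure 1 footnote reads "Approximate Total duration of CGM use would be 14-22"; no unit is printed, but the numbers match the week labels. Figure 2 screens high-risk controls at 14 weeks' gestation and typical-risk controls at 24-28 weeks, with Visit 4 at 38-40 weeks for both.

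**The concern.** One fixed number of strips is set against two follow-up lengths that differ by eight weeks. The number fits the shorter schedule closely and the longer one not at all. Early-diagnosed women are a planned part of the trial: they have their own visit and their own rows in Figure 2, and pregnancies of 14-24 weeks make up two of the four randomization strata in Section I.

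For a control without strip coverage on the early schedule, the 400, the stated frequency, the length of follow-up and Section J's unlimited supply statement cannot all hold. Two things are at stake. One is what she may have to pay. The other is how control-arm meter data late in pregnancy are read: a gap in supply could be recorded as poor compliance with fingersticks.

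**Working it through.** **Inputs.** Strips supplied: 400 (Section T). Tests per day: at least 4 (Section J), with 4 as the compliance standard (Section N). Weeks on study: 14 or 22 (Section H, Visit 4), or the gestational ages in Figure 2.

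**The plan's figure.** The protocol gives no derivation for 400, so there is nothing to reproduce. As a consistency check, 14 weeks × 7 days × 4 tests = 392, close to 400. The documents do not say that this is its basis.

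**How long 400 strips last.** 400 / 4 = 100 days; 100 / 7 = 14.3 weeks. Four a day is a minimum, so this is the longest the supply lasts at the Section J frequency. At five a day it is 400 / 5 = 80 days, or 11.4 weeks.

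**Strips needed** = weeks × 7 × 4 = weeks × 28.

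| Follow-up | Weeks | Strips needed | Against 400 |
|---|---|---|---|
| Regular, Visit 4 label | 14 | 392 | 8 spare |
| Typical risk, Figure 2, from 24 to 38-40 weeks' gestation | 14-16 | 392-448 | 8 spare to 48 short |
| Early, Visit 4 label | 22 | 616 | 216 short |
| Early, Figure 2, from 14 to 38-40 weeks' gestation | 24-26 | 672-728 | 272-328 short |

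On the 22-week schedule the shortfall is 216 / 616 = 35%, or 216 / 28 = 7.7 weeks of testing. Spreading 400 strips over 22 weeks gives 400 / 154 = 2.6 tests a day.

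**When supply ends for early controls.** The protocol's timelines do not agree on the starting gestation, so a range is needed.

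- Figure 2 starts at 14 weeks: 14 + 14.3 = 28.3 weeks.
- Visit 1b, labelled week 6 at 20-22 weeks, implies a start at 14-16: supply ends at 28.3-30.3 weeks.
- Visit 4, labelled week 22 at 38-40 weeks, implies a start at 16-18: supply ends at 30.3-32.3 weeks.

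On each of these, supply ends before the 34-36 week visit.

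**The case against.** Five points can be made for the plan.

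1. *The study may intend to supply all strips.* Section J reads that way. Section T calls the intervention arm's 50 strips a total but does not use that word for the controls' 400. The consent form, where costs may be set out, is not in the public text. This stands as a reason not to claim that anyone will certainly run out. It does not remove the inconsistency between Sections J and T.

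2. *The cost sentence may mean no cost beyond usual care.* Section J (Glucose Meter) and Section Q both describe fingerstick testing as standard of care, so a control might need these strips outside the trial. That reading is open. A reader might infer a flat contradiction of the cost promise, but the text supports only an ambiguity, because Section T does not say what the cost is additional to.

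3. *Testing frequency follows the obstetric provider.* Section H makes fasting and post-meal testing the fallback when no instruction has been given. This is a fair qualification, but Section J still states at least four a day and compliance is judged against four.

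4. *The trial outcomes are untouched.* This largely stands. HbA1c and fructosamine come from blood samples, and control CGM data come from separately supplied blinded sensors. A reader might infer that a weakened control condition favours RT-CGM. That needs women to stop testing when free strips end, and nothing in the documents shows that; routine obstetric care continues throughout.

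5. *Few women may be affected.* Section H expects enrolment mostly at 24-28 weeks, and only controls without strip coverage are concerned. This limits the weight of the point but does not answer it.

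**Conclusion.** The inconsistency is real and minor. For a control without insurance coverage for strips, 400 strips support 14.3 weeks at the stated minimum frequency. The shortfall is 216 strips on the 22-week early schedule, 272 to 328 on Figure 2's early timeline, and up to 48 for a typical-risk control enrolled at 24 weeks and followed to 40. It would therefore be wrong to treat every regular-schedule control as covered.

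The result rests on three assumptions: four tests a day throughout, 400 being the whole allotment, and follow-up to 38-40 weeks. Delivery before supply ends would avoid the shortfall. The number of women affected cannot be worked out, because the documents give neither the share without coverage nor the share enrolled early.

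The direct consequences are possible cost to participants and less interpretable control-arm meter summaries and testing-frequency measures late in pregnancy. The sample size and the HbA1c analysis are not affected, and no bias between the arms is demonstrated.

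**What to change.** Reconcile Section J (Control Group), the Section H schedule with Figure 2, and Section T. Either replace the fixed 400 with a number tied to each control's weeks from enrolment to delivery, at the testing frequency the protocol already states, or say in Section T that strips are resupplied as needed. Then make the cost sentence agree, stating whether it means no cost at all or none beyond standard care. No testing frequency or clinical rule is proposed here.

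The cost is roughly 50 to 330 extra strips per affected control (48 to 328 from the table), with no new visits or procedures.
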